- Number of pressure pain points on palpation of the masticatory muscles and in the area of the temporomandibular joints
- Number of posterior contact points
- Clinical occlusion protocol
- digital occlusion protocol determined with occlusal registrations in habitual intercuspidation; Evaluation by software GEDAS (Greifswald Digital Analyzing System) based on transparent contact areas.

Sleep-related variables:

- Sleep quality (Pittsburgh Sleep Quality Index PSQI)
- Epworth Sleepiness Scale (ESS)
- STOP-Bang questionnaire
- Oral Health Impact profile (OHIP-5)
- Apnea Hypopnea Index (AHI)
- Desaturation index (DI)
- Average oxygen saturation during sleep

Methods of data collection

The data collection is paper-based. For each patient, an analog study file is created. The main contents of the study file are the case report forms (CRF) and the questionnaires (PSQI, ESS, STOP-Bang, OHIP-5) and the AHI and EI).

The Pittsburgh Sleep Quality Index (PSQI) retrospectively asks for a four-week period the incidence of sleep disturbing events, sleep quality assessment, sleep habits, sleep latency and sleep duration, sleeping medication use, and daytime sleepiness. A total of 18 items are used for quantitative evaluation and assigned to 7 components, each of which can assume a value range of 0 to 3. The total score is the sum of the component scores and can vary from 0 to 21, with a higher score corresponding to a reduced sleep quality. There is an empirically determined cut-off value (of 5), which allows a classification into "good" and "bad" sleepers.

The Epworth Sleepiness Scale (ESS) is a short questionnaire for the detection of daytime sleepiness, in which the probability of falling asleep or falling asleep in eight typical everyday situations is retrospectively inquired. It can generally be used for sleep disorders, especially for hypersomnia, as a screening instrument for the global detection of daytime sleepiness or as an indication of the presence of hypersomnia. In addition, it is also suitable for measuring progress or success (for example in CPAP patients).

The STOP-BANG questionnaire is a screening for the presence of OSAS in the general population. A low OSAS risk exists if 0-2 answers yes, a medium OSAS risk if yes to 3-4, and high OSAS risk if yes to 5-8 questions.

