The Oral Health Impact Profile (OHIP) is a measurement tool for assessing the oral health-related quality of life in adults. It can describe the individual oral health status of patients and measure and compare disease-related burdens in the course.

The Graded Chronic Pain Scale (GCPS) questionnaire records pain intensity and the presence of functional or dysfunctional chronic pain.

The Apnea Hypopnea Index (AHI) is a measure of how many breathing pauses in the form of apneas and hypopneas a patient experiences while sleeping. The AHI is determined in the sleep laboratory via a polysomnographic recording. Depending on the value of AHI, a distinction is made between mild, moderate and severe sleep apnea.

The desaturation index (DI) is the number of oxygen desaturations per hour of sleep. The questionnaires (PSQI, ESS, OHIP-5, STOP-BANG, GCPS) are completed by the investigators in the form of an interview with the patient. AHI and DI are collected in the sleep laboratory.

Occlusion protocol: The tooth contacts between upper and lower jaw are recorded once with thin (ShimStock) slides for each tooth during the clinical examination. Furthermore, bite registrations in habitual intercuspidation (centric occlusion) are created from thinly flowing, addition-crosslinked silicone and scanned with a document scanner for evaluation in transmitted light. Layer thicknesses $\leq 20 \mu\text{m}$ are interpreted as occlusal contacts and assigned to the anatomical structures of the chewing surfaces (Greifswald Digital Analyzing System).

Functional Examination is designed to record masticatory jaw joint disorders based on a detailed history and subsequent clinical examination, palpation and orofacial inspection. For this purpose, a current and standardized examination procedure, the Diagnostic Criteria for TMD (DC/TMD) is used. This research toolkit also includes the Questionnaire on Chronic Pain Grading (GCPS), Jaw Functional Limitation Scale (Jaw Functionality), and Oral Behavior Checklist.

Treatment group 1:

Patients with snoring and OSAS, Therapy SomnoDent Fusion™ Fusion MAD with sliding side wings (F-MAD).

Picking up to reach a 5 mm incisor distance using George Gauge with a lower jaw advancement of 5 mm with insertion of the MAD up to a final titrated mandibular advancement in the therapy phase.

Treatment group 2:

Patients with snoring and OSAS. Therapy with MAD type H-MAD with lateral hinges according to Herbst.

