All patients received a structured general and somnological anamnesis and examination (height, weight, BMI, ESS, STOP-BANG, PSQI) in a first visit to the sleep laboratory. In addition, a stationary polysomnography or an outpatient polygraphy was performed there. Patients were referred to specialist dental practices for the preparation and integration of a MAD based on the diagnosis of sleep medicine for treatment of sleep apnea syndrome or snoring.

Baseline examination

Patient history and the dental status and periodontal screening index (PSI) are used to check inclusion and exclusion criteria for splint therapy. Subsequently, a functional status, occlusion protocol clinical and digital (GEDAS, Greifswald Digital Analyzing System), the questionnaires for pain chronification (GCSP) and quality of life (oral health impact profile, OHIP-5) are included.

To assess the health of the teeth and to ensure the success of treatment, an X-ray survey (panoramic radiograph) must be available before the treatment, which is not older than 6 months. Such an X-ray photograph can be made by the dentist or the specialized dental practice.

The functional status is determined by means of a standardized functional finding (DC / TMD). The questionnaires are based on validated recommendations. All examination procedures are part of the routine patient diagnostics, which have been standardized for the individual practices for this project.

Randomization

The randomized grouping into blocks at a ratio of 1: 1 takes place over sealed envelopes containing the allocation key for the respective MAD. The assignment is stratified according to gender because gender is a strong predictor of sleep disorders and also temporomandibular dysfunctions.

Impression taking

Subsequently, the upper and lower jaws are molded to make the respective therapeutic splints and the protrusion registrations are taken. The starting position of the mandibular protrusion is set to 5 mm by default.

Integration of the MAD (start of treatment)

The laboratory-made MAD (F-MAD / H-MAD) is integrated (with a mandibular protrusion of 5 mm) and checked for a comfortable fit. Here, we paid attention to a

surface contact between OK-UK splint, and a tension-free fit of the splint portions on the rows of teeth. If necessary, interfering contacts are ground in. The patient is instructed to always wear the splint during sleep.

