The evaluation of the primary (and also the secondary) target variable is carried out according to the power analysis using ordinal regression as a generalization of the Wilcoxon-Mann-Whitney test. Adjustments are made according to sex as a stratification variable, age ("restricted cubic splines" with 3 nodes, which requires 2 coefficients), the baseline value of the respective target variable, the centers, the school education and, if appropriate, the blocks of randomization.

The intention-to-treat analysis set includes all patients assigned to one of the two groMAD and the built-up track; the "per protocol" set includes all patients with supported splints, primary target size data at 24 months and no relevant deviations from the study protocol. Sensitivity analyzes are performed with replacement of missing values via multiple imputation.

An interim evaluation is not planned.

Subgroup analyzes are not planned.

The 95% confidence interval is interpreted; the list of primary and secondary target sizes listed above allows $\alpha = 0.05$ to be left uncorrected (Cook & Farewell) (4).

At the University Medicine Greifswald, Center for Dental, Oral and Maxillofacial Surgery (ZZMK) the blinded evaluation of the data takes place.

This study is conducted with particular attention to the contents of the following laws and guidelines:

- Declaration of Helsinki in its current version (Fortaleza, 2013)
- Medical Devices Act - MPG
- Medical Device Operator Ordinance - MPBetreibV
- State Data Protection Act - DSG M-V
- General Data Protection Regulation - EU GDPR

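### The only named pre-treatment ESS and PSQI scores come from the sleep-laboratory visit, with no limit on their age: a weaker baseline covariate for two secondary outcomes, but no bias between devices

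*Combined protocol and SAP*

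**What the plan says.** The section Sleep Laboratory reports that every patient had a structured history and "examination (height, weight, BMI, ESS, STOP-BANG, PSQI) in a first visit to the sleep laboratory", followed by a sleep recording and then referral to the dental practice.

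The section Baseline examination, at the dental practice, covers the dental and functional findings and the occlusion protocol. For questionnaires it says that "the questionnaires for pain chronification (GCSP) and quality of life (oral health impact profile, OHIP-5) are included". ESS and PSQI are not named there.

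All four control appointments (4 weeks, then 6, 12 and 24 months) collect ESS, OHIP-5 and PSQI together.

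Statistical evaluation analyses primary and secondary variables by ordinal regression between the two devices, with "the baseline value of the respective target variable" among the covariates.

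The panoramic radiograph "must be available before the treatment, which is not older than 6 months". No such limit is given for the sleep-laboratory scores.

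Methods of data collection adds two facts: the PSQI "retrospectively asks for a four-week period", and "The questionnaires (PSQI, ESS, OHIP-5, STOP-BANG, GCPS) are completed by the investigators in the form of an interview with the patient". The second sentence names no visit.

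**The concern.** OHIP-5 has a dental baseline that matches its follow-up. ESS and PSQI, collected beside it at every control appointment, do not. Their only scheduled pre-treatment values come from a different place, at an earlier time of unstated distance. Because the PSQI covers four weeks, an old score describes an old month.

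The mode of collection may also differ. Recruitment is at dental or oral surgery clinics, the sleep centres appear as referrers, and the training described under Calibrating the examiner is for the dentists. Nothing shows that sleep-laboratory staff use the investigator interview.

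The eligibility criteria do not mention earlier or intervening treatment for sleep apnoea, so the documents neither describe nor exclude such treatment between the two visits. At stake are the precision of the adjusted device comparison for ESS and PSQI, and the meaning of any before-after figure reported for either device.

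**Working it through.** **The plan's own figure.** The only sample-size figure is for the pain scale: difference 1, SD 2, two-sided alpha 0.05, power 0.90, Wilcoxon-Mann-Whitney test with a logistic parent distribution, 78 per arm. With the logistic relative efficiency π²/9 = 1.097, 78 per arm gives power 0.902 and 77 gives 0.898, so 78 is reproduced. ESS and PSQI do not enter this figure, and the plan states none for them.

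**Schedule, side by side.**

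| Questionnaire | Sleep laboratory | Dental baseline | Four control appointments |
|---|---|---|---|
| ESS | yes | not named | yes |
| PSQI | yes | not named | yes |
| OHIP-5 | not named | yes | yes |

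**Is the device comparison biased?** The sleep-laboratory score precedes allocation, so its age, and anything that happened since, is balanced between the arms in expectation. A simulation (4,000 runs, 78 against 78, linear baseline-adjusted model) checked this. All inputs were assumed and alike in both arms: gap uniform over 0 to 18 months, drift of 0.05 points per month, 30% of patients with interim therapy worth 1.5 points, SD 4, and a baseline correlation that decays with the gap.

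- True difference 1.5: mean estimate 1.50.
- True difference 0: mean estimate -0.01, type I error 4.8%.

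**Before-after change within one arm.** In the same scenario the reference device was given an effect of -2.0. The mean gap is 9 months, so drift adds 9 × 0.05 = 0.45, and interim therapy adds 0.30 × 1.5 = 0.45. The expected observed change is -2.0 - 0.45 - 0.45 = -2.9, and the simulation gave about -2.9. This shows the mechanism only. Its size depends on the assumed inputs.

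**Precision.** In a linear model, adjusting for a baseline with correlation r to follow-up leaves residual variance proportional to 1 - r². The planned model is ordinal, so this is an approximation. No value of r is given in the documents; all are assumed.

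- 1 - 0.7² = 0.51; 1 - 0.6² = 0.64; 1 - 0.5² = 0.75; 1 - 0.4² = 0.84.

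| Fall in r | Variance ratio | Interval width ratio |
|---|---|---|
| 0.5 to 0.4 | 0.84 / 0.75 = 1.12 | √1.12 = 1.06 |
| 0.7 to 0.6 | 0.64 / 0.51 = 1.25 | 1.12 |
| 0.7 to 0.4 | 0.84 / 0.51 = 1.65 | 1.28 |

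Expressed as the standardised difference detectable with 78 per arm at 90% power, (1.960 + 1.282) × √(2(1 - r²)/78): 0.371 at r = 0.7, 0.415 at 0.6, 0.450 at 0.5 and 0.476 at 0.4.

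**The case against.** The strongest reply is that the plan contains no before-after analysis of ESS or PSQI. The three hypotheses compare the devices on pain, pressure-pain areas and contact points. Only the primary pain variable is defined as a change, and the secondary variables go into a comparison of randomised arms. A reader might infer from the schedule that the ESS and PSQI results would mix the device effect with elapsed time and interim therapy. For the planned comparison the documents do not support that, and this part of the reply stands in full. Intervening CPAP or weight loss is likewise only a possibility that the plan leaves open; no passage describes it, and nothing indicates that long gaps are common.

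A reader might also infer that patients without a sleep-laboratory score would be lost from the adjusted model. The documents do not support this either: the Sleep Laboratory section says that all patients received the assessment, and sensitivity analyses with multiple imputation are planned.

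The visit lists may also be incomplete. The pain scale itself is not named in any of them, nor are AHI and the desaturation index at the control appointments. The sentence on investigator interviews could therefore be read as covering the dental baseline. This stands in part: that ESS and PSQI are taken only in the sleep laboratory is a reading of the schedule, not a statement in it. But the interview sentence says who completes the questionnaires, not when, so it does not settle the matter.

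Finally, the precision figures rest on assumption, and a lower correlation would apply mainly to patients with long gaps rather than to the whole sample. That stands, and it is why small falls in r are shown beside the large one.

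**Conclusion.** The concern holds in a limited form. As scheduled, the named pre-treatment ESS and PSQI scores come from the sleep laboratory, before referral, with no limit on their age. The randomised contrast between F-MAD and H-MAD remains unbiased. What may be lost is precision on two secondary outcomes: about 6% to 28% wider intervals over the assumed falls in correlation, if the lower correlation applied to the whole sample and the linear approximation carried over to the ordinal model. The true loss cannot be computed from the documents and could be smaller. Separately, any descriptive before-after change in ESS or PSQI could not be attributed to the device alone. The primary outcome, its sample size and the three stated hypotheses are untouched. This is an inexpensive improvement, not a defect that threatens the trial's conclusions.

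**What to change.** In Baseline examination, add ESS and PSQI next to OHIP-5, completed before the randomisation envelope is opened and in the same interview mode as at the control appointments. In Statistical evaluation, state that these scores are the baseline values for the two outcomes. Keep the sleep-laboratory scores as descriptive data, each with its date.

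The cost is two short questionnaires, a few extra minutes per patient, at a visit that already takes place. It has to be done before fitting, because a contemporaneous baseline cannot be recovered once treatment has begun.

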All patients receive an extended guide to jaw gymnastics with the instruction to do it in the morning after waking up and in the evening before falling asleep.

First control appointment (4 weeks after incorporation)

Four weeks after incorporation, the titration phase begins, d. H. the slow adjustment of mandibular advancement to optimize sleep medical parameters while minimizing unwanted side effects. The feed rate should be adjusted until clinical and sleep medical parameters are optimal or the patient can no longer tolerate further advancement.

The functional findings, the occlusion protocol, the questionnaires ESS, OHIP-5 and PSQI are collected.

Second control appointment (6 months after start of therapy)

Six months after the start of treatment, another examination is carried out in which the functional findings, the occlusion protocol and the questionnaires ESS, OHIP-5 and PSQI are collected.

Third control appointment (12 months after start of therapy)

A third check is made 12 months after the start of therapy. The functional findings, the questionnaires ESS, OHIP-5 and PSQI, the occlusion protocol, the bite registration for scanning and contact point analysis (GEDAS, Greifswald Digital Analyzing System) are collected.

Fourth control appointment (24 months after start of therapy)

The last examination is 24 months after the start of therapy. The functional findings, the questionnaires ESS, OHIP-5 and PSQI, the occlusion protocol, the bite registration for scanning and contact point analysis (GEDAS, Greifswald Digital Analyzing System) and new models are collected.

Sample size estimation

Determine the required sample size based on the numerical pain scale 0-10 for the primary target variable. Norms are pain scores of 3-5 (myofascial pain) in patients with temporomandibular dysfunction (TMD). To determine a mean difference of 1 level (standard deviation of 2) (1, 2) between the MAD, they must each comprise 78 patients.

Test method:

Wilcoxon-Mann-Whitney test with a two-sided $\alpha = 0.05$, a power = 0.90 assuming the family of logistic distributions (G * Power, version 3.1.)

The net sample consists of 156 persons. The annual dropout is 10% (3), so that for a study period of 2 years a total sample of 194 persons must be calculated (194 - 20 = 174 after 1 year, 174 - 18 = 156 after 2 years).

Statistical evaluation

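### Patients lost before month 6 have no pain score from after titration began, and stopping the device because of a side effect is not a defined outcome

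*Combined protocol and SAP*

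**What the plan says.** Under *Impression taking*: "The starting position of the mandibular protrusion is set to 5 mm by default". Under *First control appointment*: "Four weeks after incorporation, the titration phase begins". The end of titration has no date: "The feed rate should be adjusted until clinical and sleep medical parameters are optimal or the patient can no longer tolerate further advancement". At week 4, "The functional findings, the occlusion protocol, the questionnaires ESS, OHIP-5 and PSQI are collected".

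The next entry is the *Second control appointment*: "Six months after the start of treatment, another examination is carried out in which the functional findings, the occlusion protocol and the questionnaires" are recorded. Further appointments follow at 12 and 24 months. No titration visit, unscheduled visit or early-termination visit is described. *Primary outcome variable* places the 0–10 pain rating at the follow-up appointments.

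The primary and secondary outcome lists contain no adverse events, device discontinuation, reason for stopping or tolerance limit. Under *Data management*, the study file holds an adherence assessment, and fields left empty for lack of information need a comment. The case report form is not part of the documents.

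In *Statistical evaluation*, the per-protocol set "includes all patients with supported splints, primary target size data at 24 months and no relevant deviations". Multiple imputation is planned as a sensitivity analysis. In *Sample size estimation*: "The annual dropout is 10% (3), so that for a study period of 2 years a total sample of 194 persons".

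**The concern.** The trial exists to find side effects of two devices over two years and to compare them. The exposure most likely to produce those side effects begins at week 4, when advancement moves beyond its fixed start. The plan itself expects some patients to reach a limit of tolerance. Yet no visit list or outcome records that this happened, and no examination is scheduled for about five months after titration starts.

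Two things are at stake. First, patients who leave the study in that window contribute no pain score that reflects titration. Second, stopping a device because of pain, joint trouble or a bite change is a direct measure of what the trial studies, and the plan does not count it by arm. A stop date or reason that was never collected cannot be recovered at the analysis stage.

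**Working it through.** **The plan's own figures.** Inputs from *Sample size estimation*: difference 1, SD 2 (standardised difference 0.5), two-sided alpha 0.05, power 0.90, Wilcoxon-Mann-Whitney test, logistic family. A two-sample t calculation with n scaled by the logistic relative efficiency π²/9 gives 78 per group (power 0.902), or 156 net. Losses: 194 − 20 = 174, then 174 − 18 = 156, so 38 in total. The direct formula 156 / 0.9² = 192.6 agrees within rounding. All figures reproduce, and nothing in this point changes them.

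**Length of the gap.** Month 6 is week 26, and 26 − 4 = 22 weeks.

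**Patients affected.** Assume that the 20 year-1 losses are even over 52 weeks:

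- before week 4: 20 × 4/52 = 1.5
- week 4 to month 6: 20 × 22/52 = 8.5
- after month 6: 38 − 20 × 26/52 = 28

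The parts sum to 38. A constant 10% annual rate gives nearly the same number in the gap: 194 × (0.9^(4/52) − 0.9^(1/2)) = 8.4. So about 8 of 194 (4%) are lost in the gap. If all year-1 losses fell there, it would be 20 (10%). The 28 later leavers could have at least a month-6 score.

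**What the week-4 score reflects.** The order of examination and first adjustment at week 4 is not stated. Either way, the score describes the preceding four weeks at 5 mm. The pain rating is not named in any visit list; that it is taken at week 4 is inferred from the primary outcome definition.

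**What imputation can use.** For someone lost in the gap, the only on-treatment data come from week 4. Imputation under missing-at-random treats that patient as having the same later pain distribution as a patient who stayed, in the same arm and with the same earlier data. If the patient left because of what happened after week 4, that assumption fails, and nothing the plan defines would show it.

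**Does the arm split matter?** A simulation on assumed inputs (logistic scores, true difference 1, SD 2, completers only, pain-related leavers being the highest scorers in their arm, other losses random, 156 completers) gives:

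| Leaving for pain, F-MAD / H-MAD | Observed difference |
|---|---|
| 0% / 0% | 1.00 |
| 5% / 5% | 1.00 |
| 7.5% / 2.5% | 0.80 |
| 5% / 0% | 0.77 |

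This covers pain-related leaving over the whole trial and does not isolate the 22-week gap. It shows only that the effect comes from an imbalance between arms. The reverse imbalance would push the estimate the other way.

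**The case against.** A reader might infer more than the text supports.

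- *Everyone who stops the device leaves with only a pre-titration score.* No section says that stopping ends follow-up. The intention-to-treat set rests on assignment and, as far as the wording can be read, a fitted splint, not on continued wear. A patient who stops in month 3 is still due at months 6, 12 and 24. The missing score concerns only patients lost to the study before month 6.
- *Nothing about stopping is captured.* The study file has an adherence assessment, empty fields must be commented on, the per-protocol set needs wear status, and the functional examination at month 6 includes a history. Some stops will surface this way, and the unseen case report form may hold more. What stands is that no date, reason, outcome or analysis is defined.
- *Early leavers are analysed at their mildest score.* That would be carrying the last observation forward. The plan names multiple imputation, where week 4 is a predictor and not the imputed value. A specific loss of between-device difference calculated that way does not follow.
- *The losses are caused by pain.* The 10% dropout has no stated cause.

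Two further objections are fair. *Insurance* says that follow-up follows clinical routine without extra visits, so the visit spacing is a deliberate choice; the fix must not depend on new visits. Patients may also withdraw without giving a reason, so a reason can be recorded only when offered.

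**Conclusion.** The point holds in two parts. Patients lost before month 6 have no pain score from after titration began: about 8 of 194 between week 4 and month 6 if year-1 dropout is even, and at most 20 if all planned year-1 losses fall there. In addition, discontinuation, its date and its reason are not a defined outcome at any time in the trial, so the plan provides no comparison of side-effect stopping between devices. The second part is the more important, since it applies throughout the two years and to stoppers who stay in follow-up as well.

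The size and direction of any bias in the pain comparison are not established. They depend on how stopping differs between arms, which the documents do not give. The conclusion also assumes that the case report form has no stop field linked to an analysis, which cannot be checked. The sample size is unaffected. This is an inexpensive improvement that should be made, not a flaw that invalidates the design.

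**What to change.** 1. Whenever the device is stopped, and at any titration contact that takes place anyway, record the date, the 0–10 pain rating, device stopped yes/no, and the reason if the patient offers one (pain, joint or bite change, lack of effect, other).
2. At months 6, 12 and 24, ask about stopping since the last visit.
3. List device stopped because of a side effect as a secondary outcome, reported as proportion and time by arm.
4. State that patients who stop the device and still consent stay on the remaining control dates.
5. Include stop status and reason in the imputation model.

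The cost is a little more site paperwork and one more secondary outcome. No visit is added. The plan does not describe titration contacts, so how many such entries there will be is unknown; items 2 to 4 work without them. The change concerns data collection and analysis only and alters no treatment rule.

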Sleep fragmentation caused by respiratory disorders during sleep and wakefulness reactions (arousals) can lead to daytime sleepiness and concentration disorders. In the longer term untreated arousals and apneas are associated with an increased risk for arterial hypertension, stroke, myocardial infarction, diabetes mellitus and libido loss.

OSAS management includes positive pressure ventilation with continuous positive airway pressure (CPAP) masks, mandibular advancement of the mandible with mandibular advancement devices (MAD), weight loss, ear, nose and throat surgical procedures, bimaxillary or mandibular remodeling osteotomies, and neurostimulation procedures of the hypoglossal nerve.

Several studies have shown that the use of MADs is inferior in reducing the severity of OSAS in comparison to CPAP therapy, but its efficacy is comparable and preferred by patients in mild to moderate OSAS.

Due to the forward displacement of the lower jaw for several hours at night, similar symptoms as in temporomandibular dysfunction (TMD) patients may occur. The symptoms may be pain or stiffness on the masticatory muscles or temporomandibular joints.

This study aims to identify possible side effects in the temporomandibular system that occur during the course of two years of nocturnal MAD delivery. Two different

appliance systems are compared in terms of construction height (bite elevation) and protrusion mechanics: the H-MAD™ with a hinge system according to Herbst and the SomnoDent Fusion™ (called F-MAD) with sliding side wings.

Hypotheses

1. F-MAD significantly increases pain in the craniofacial area (primary target variable) compared to H-MAD.
2. The F-MAD leads to a significantly increased number of pressure-pain areas of the masticatory muscles and temporomandibular joints compared to the H-MAD.
3. The F-MAD has a higher loss of posterior contact points than the H-MAD.

Study design

Multicenter, randomized two-arm Phase IV study with active control group, stratified by gender, unblinded with respect to the examiner, blinded to the patient and statisticians in the evaluation.

Primary outcome variable

The primary outcome variable is defined as the change of orofacial pain after applying the MAD as measured by numeric rating scale (NRS; 0-10, 0: no pain, 10: worst imaginable pain) at the time of the follow-up appointments.

Secondary outcome variables:

Dental variables:

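### Does leaving the randomisation blocks as an optional term in the primary ordinal model undermine its 95% confidence interval?

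*Combined protocol and SAP*

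**What the plan says.** The Statistical evaluation section specifies ordinal regression, as a generalisation of the Wilcoxon-Mann-Whitney test, for the primary and secondary variables. On covariates it says "Adjustments are made according to sex as a stratification variable", then adds a three-knot age spline (noting that this uses two coefficients) and "the baseline value of the respective target variable, the centers, the school education and, if appropriate, the blocks of randomization". On inference it says "The 95% confidence interval is interpreted", with alpha left at 0.05 uncorrected.

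The Randomization section says "The randomized grouping into blocks at a ratio of 1: 1 takes place over sealed envelopes" and "The assignment is stratified according to gender". It gives neither the block size nor the number of blocks, and does not say whether envelope lists are central or held at each clinic. Under Study design the examiner is unblinded, and the trial is "blinded to the patient and statisticians in the evaluation". Under Sample size estimation, "The net sample consists of 156 persons".

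**The concern.** Three things are missing for the block term: a criterion for including it, a coding (fixed or random), and a block size from which to judge the number of parameters. Blocks stand in the list beside sex, centres and education, which would ordinarily be fixed factors, so an analyst could code blocks the same way.

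In a proportional-odds model fitted by maximum likelihood, many nuisance coefficients each supported by a few patients push a non-null treatment log odds ratio away from zero and make its standard error too small. Because the interval is the stated basis of interpretation, under-coverage would go straight to the trial's conclusion. The models with and without fixed blocks could also disagree on significance in the same data. In addition, blocks drawn within gender would absorb the separate sex coefficient, although that does not bias the treatment effect.

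**Working it through.** **Inputs from the document.** NRS 0–10; difference 1, SD 2, two-sided alpha 0.05, power 0.90, logistic family; 78 per group, 156 net, 194 gross; 7 centres; 1:1 blocks within gender.

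**The plan's own figure.** Normal approximation: n = 2(1.960 + 1.282)² × 2² / 1² = 84.06 per group. Dividing by the Wilcoxon efficiency for a logistic parent, π²/9 = 1.097, gives 76.7. With the noncentral t, power is 0.898 at 77 and 0.902 at 78, so 78 per group reproduces. Gross: 156 / 0.9² = 192.6, that is 193, or 194 for equal groups. The sample size is not affected by this point.

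**Effect on the model scale.** A logistic variable with SD 2 has scale 2√3/π, so one point is π/(2√3) = 0.907 logits, an odds ratio of 2.48.

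**Parameter count.** Treatment 1 + sex 1 + age 2 + baseline 1 + centres 6 + education 2 (three levels assumed) = 13 slopes. Fixed blocks would add roughly 156/4 = 39 coefficients for blocks of 4, 156/6 = 26 for blocks of 6, about 16 for blocks of 10 and about 8 for blocks of 20.

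**Simulation with fixed block indicators.** Assumptions not in the document: the block sizes, the sex split, three education levels, one outcome per patient, two gender lists across all centres, and no true block effect. Simulation A has random loss from 194 to 156 (4,000 runs per cell). Simulation B has 156 in complete blocks (2,000 runs per cell).

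| Block size | A: type I error, with / without blocks | A: coverage with blocks | B: type I error with blocks | B: coverage with blocks |
|---|---|---|---|---|
| 4 | 0.130 / 0.066 | 77.9% | 0.117 | 82.4% |
| 6 | 0.102 / 0.064 | 86.0% | 0.098 | 87.1% |
| 8 | 0.094 / 0.059 | 88.5% | 0.073 | 91.3% |
| 10 | 0.083 / 0.065 | 89.3% | 0.086 | 89.6% |
| 20 | 0.075 / 0.069 | 92.1% | 0.056 | 92.9% |

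Coverage is at the planned effect. Without blocks it is about 93–94% in A and 92.8–94.8% in B; type I error without blocks in B is 0.051–0.064. A further run gave coverage of 76%, 89% and 92% for blocks of 4, 10 and 20, against 92–94% without. Blocks of 2 would be much worse (55.9% in B).

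Three readings follow.

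- The model without blocks is itself slightly off nominal, because of its other slopes. The blocks' own share is therefore the with-minus-without difference. In A, the type I excess is 0.130 − 0.066 = 0.064 for blocks of 4, 0.083 − 0.065 = 0.018 for 10 and 0.075 − 0.069 = 0.006 for 20.
- In B with blocks of 4, the median odds ratio is 3.16 against a true 2.48. With no true effect it is 1.00, and only the spread is misjudged (empirical SD 0.394, mean model SE 0.311).
- In A at the planned effect, the two models disagree on significance in 6.2% of trials for blocks of 4 and 2.6% for blocks of 20.

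**The two sensible ways to follow the sentence.**

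- Random block intercept (3,000 runs): type I error with / without blocks is 0.067 / 0.063 (blocks of 4), 0.059 / 0.055 (6) and 0.068 / 0.067 (10), with mean log odds ratio 0.96–0.97. That is essentially no inflation.
- Blocks omitted although a real block effect exists (assumed SD 0.5 logits, 2,000 runs): type I error 0.053–0.056. Power is 0.854 against 0.864 with a random intercept (blocks of 4), and 0.856 against 0.868 (blocks of 10). These gaps are within simulation error.

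**The case for a change.** The best case for a change is that the gap is certain and closing it costs one clause. The list invites fixed coding, the interval is what will be interpreted, small blocks are not excluded, and the same model serves the secondary variables. Blinding the statisticians stops a choice made on the direction of the result, but it does not repair an interval that under-covers. With fixed blocks and a separate sex term, the sentence cannot even be fitted in full.

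The missing criterion and coding stand, and so does the arithmetic, given fixed coding and small blocks. The step from there to a flawed primary analysis does not. Harm needs three things together, none of which the plan states: that blocks are judged suitable for inclusion, that they are coded as fixed indicators, and that they are small. An analyst facing dozens of block coefficients and an inestimable sex term has a plain reason to judge the term unsuitable, and the conditional wording allows exactly that. The authors, who count spline coefficients in the same sentence, evidently have parameter numbers in mind.

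Asking for the block size is no improvement. In one combined protocol and SAP, with unblinded examiners and sealed envelopes, printing it could make allocations easier to predict. Choosing between deletion and a random intercept is partly preference, since both perform well.

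**Conclusion.** No change follows. The block term is an optional covariate left to the analyst's judgement, and both reasonable ways of exercising that judgement give a sound interval. The damaging version, fixed indicators with small blocks, would lower coverage to about 76–82% for blocks of 4, but the plan does not call for it. By blocks of 20 the difference from omitting blocks is slight.

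These percentages are illustrative. They rest on assumed block sizes, two gender lists spanning all centres, and one outcome per patient, whereas the plan measures pain at several follow-up visits. Lists held at each clinic were not simulated. The conclusion depends less on the exact figures than on two facts: the plan's wording permits omission, and sex, the only stated stratification factor, stays in the model together with centre.
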